## **Background and Introduction**

Parkinson's disease (PD) is characterized by the gradual onset of motor symptoms such as bradykinesia, rigidity, tremor, gait difficulties and postural instability, as well as non-motor symptoms such as cognitive impairment and autonomic dysfunction among others [1]. Neurogenic orthostatic hypotension (nOH) is the main clinical manifestation of cardiovascular autonomic dysfunction [2]. The arterial baroreflex allows for beat-to- beat regulation of the blood pressure and heart rate via differential modulation of its cardiovagal (parasympathetic) and noradrenergic (sympathetic) efferent limbs [3]. Several mechanisms may contribute to nOH in PD including baroreflex-cardiovagal and baroreflex-sympathetic noradrenergic failure [2]. The prevalence of nOH in PD increases with age and disease duration; however, several studies have documented that nOH may appear early in the course of PD and reported prevalence of nOH in PD ranges from 30% to 65% [4, 5]. The presence of nOH in PD is associated with poor outcomes related to cardiovascular events, increased morbidity and mortality, more rapid disease progression, cognitive impairment, and falls [6].

Levodopa is a precursor of dopamine and is the treatment of choice to treat the motor symptoms of PD; however, the effect of levodopa on cardiovascular autonomic function in PD is poorly understood. Orthostatic hypotension has been documented as a potential side effect of levodopa in different studies [7, 8]. As a result, clinicians may be reluctant to prescribe levodopa in patients with PD with nOH (PD+OH), which leads to suboptimal management of motor symptoms. On the other hand, several studies failed to show any clear relationship between levodopa and orthostatic hypotension in patients with PD [9-12]. Important limitations of prior studies include the lack of detailed investigation of baroreflex cardiovagal and sympathetic noradrenergic functions and the fact that the same patients were not tested on and off levodopa.

We propose to investigate the effects of levodopa on cardiovascular autonomic function in patients with PD+OH and PD without nOH (PD-OH) by performing standardized autonomic testing in the same patients on and off levodopa.

# **Purpose and Objectives**

We propose to investigate the effects of levodopa on cardiovascular autonomic function in patients with Parkinson's Disease with orthostatic hypotension (PD+OH) and Parkinson's Disease without neurogenic orthostatic hypotension (PD-OH) by performing standardized autonomic testing in the same patients on and off levodopa.

## Objectives

AIM #1. The primary objective of the study is to investigate the effect of levodopa on cardiovascular autonomic function in participants with PD (with and without OH) Participants with PD+OH and PD-OH will undergo autonomic testing of baroreflex cardiovagal and sympathetic noradrenergic functions on and off of levodopa on two separate days. The primary endpoint will be the change in systolic blood pressure from supine to tilt at 3 minutes. Results of autonomic testing on levodopa will be compared to testing off levodopa in all participants. Each patient will be his or her own control. Secondary endpoints will include validated indices of baroreflex cardiovagal and baroreflex sympathetic noradrenergic functions. Although levodopa may have a mild hypotensive effect, we hypothesize that levodopa will not induce or worsen the drop in blood pressure from supine to tilt at 3 minutes and will not worsen neurogenic orthostatic hypotension. Planned secondary endpoints will also investigate the differences in orthostatic vital signs with active standing and tilt table testing in patients with PD and the relationship between autonomic testing and the orthostatic symptom severity questionnaire.

**AIM #2.** Determine if levodopa has a different effect on cardiovascular autonomic function in participants with PD+OH compared to participants with PD-OH

The data from autonomic testing performed for AIM#1 will be used to assess AIM#2. The primary endpoint for AIM#2 will be indices of baroreflex cardiovagal and noradrenergic function. We hypothesize that levodopa will not alter baroreflex cardiovagal and sympathetic noradrenergic functions in either PD+OH or PD-OH.

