# Statistical Methods, Data Analysis and Interpretation

Summary statistics will be used to describe demographic and clinical variables. A sample size of 40 will achieve a power of 80% and a level of significance of 5%, for detecting a mean of 8 mmHg in ΔSBP-3' between the ON and OFF states with a within subject standard deviation of 20 mmHg based on published data on the effect of levodopa on supine and standing blood pressure in people with PD. The main statistical analysis will be conducted using mixed-effects regression models (linear mixed models), which will allow for the correlation of repeated measures within subjects. The response variable in our models will be ΔSBP-3', and the primary predictors will be the ON vs. OFF levodopa state and the period (visit 2 versus visit 3). A random intercept will be included for each subject to account for the within-subject correlation. For analyses of secondary outcomes, we will fit a mixed effect model and adjust the p value for multiple comparisons using the Hochberg multiple comparison procedure. Changes in blood pressure and heart rate with active standing and indices of baroreflex cardiovagal and sympathetic noradrenergic function OFF levodopa will be compared between PD+OH and PD-OH with Student t tests.

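### The hypotheses are of no worsening and no alteration, but the plan gives only a test for a difference, with no margin or interval rule and no specified ON–OFF contrast by group

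*Combined protocol and SAP*

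**What the plan says.** In the combined protocol and SAP, the Objectives section states the Aim 1 hypothesis as "we hypothesize that levodopa will not induce or worsen the drop in blood pressure from supine to tilt at 3 minutes", and adds that levodopa "will not worsen neurogenic orthostatic hypotension". The comparison is within participant and pooled over both groups: "Results of autonomic testing on levodopa will be compared to testing off levodopa in all participants". Aim 2 asks whether the effect of levodopa differs between PD+OH and PD-OH. Its hypothesis is: "We hypothesize that levodopa will not alter baroreflex cardiovagal and sympathetic noradrenergic functions in either PD+OH or PD-OH".

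The section Statistical Methods, Data Analysis and Interpretation gives 40 participants, 80% power and "a level of significance of 5%, for detecting a mean of 8 mmHg", "with a within subject standard deviation of 20 mmHg". For ΔSBP-3' a linear mixed model is planned, in which "the primary predictors will be the ON vs. OFF levodopa state and the period (visit 2 versus visit 3"). Secondary outcomes get a mixed model whose terms are not listed, and the plan will "adjust the p value for multiple comparisons using the Hochberg multiple comparison procedure". The only comparison of PD+OH with PD-OH that is described is a t test on values measured OFF levodopa.

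Neither section gives a non-inferiority or equivalence margin, a criterion for a confidence interval, or a statement of which result would confirm the hypotheses. The sidedness of the 5% is not stated.

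**The concern.** The first Aim 1 hypothesis is of the non-inferiority type (no worsening). The Aim 2 hypothesis is of the equivalence type (no alteration in either direction). A test for a difference can reject equality, but failing to reject does not show that the difference is small. The investigators expect a result near zero, and for that result the plan does not say what may be concluded.

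This bears on the purpose of the study. The Background and Introduction explains that worry about hypotension can lead to under-treatment of motor symptoms in PD+OH. The useful answer is therefore how large a worsening the data rule out, overall and in PD+OH. Without a rule set beforehand, an inconclusive interval could be reported as agreeing with the hypothesis, and a margin chosen after the data are seen would carry little weight.

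Aim 2 has a further gap. A comparison of OFF values between groups contains no levodopa effect, so it cannot show whether that effect differs by group.

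**Working it through.** **Inputs.** From Statistical Methods: n = 40, difference to detect 8 mmHg, alpha 5%, power 80%, SD 20 mmHg. Two things are unstated: whether the test is one- or two-sided, and whether 20 is the SD of the ON–OFF difference or the within-subject SD of one measurement. In the second case the SD of the difference is 20 × √2 = 28.3. Worsening means a larger drop ON than OFF.

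**Reproducing the sample size.** For a paired mean difference, n = (SD_diff × (z_alpha + z_power) / 8)². With SD_diff 20 and one-sided 5%: (20 × (1.645 + 0.842) / 8)² = 38.6, so 39, or 41 with the t distribution. The other columns use a paired t test with 39 degrees of freedom. The cut-off is t × SD_diff / √40.

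| Reading | n for 80% (normal / t) | Power at n = 40 | True 8 mmHg missed | Cut-off (mmHg) | Upper bound at the cut-off (2 × cut-off) |
|---|---|---|---|---|---|
| SD_diff 20, one-sided 5% | 39 / 41 | 80% | 20% | 5.33 | 10.7 |
| SD_diff 20, two-sided 5% | 50 / 52 | 69% | 31% | 6.40 | 12.8 |
| SD_diff 28.3, one-sided 5% | 78 / 79 | 54% | 46% | 7.53 | 15.1 |
| SD_diff 28.3, two-sided 5% | 99 / 101 | 41% | 59% | 9.05 | 18.1 |

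Only the first row reproduces 40. The two-sided case with normal quantiles also gives 40 if 20 is the SD at each visit and the two visits correlate at 0.6 (SD_diff = 20 × √0.8 = 17.9). That needs a correlation the plan does not give, and it does not match the plan's description of the SD as within subject.

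**What non-significance leaves open.** In the first row the standard error is 20 / √40 = 3.16. An observed worsening just under 5.33 mmHg is non-significant. Its matching one-sided 95% upper bound is 5.33 + 5.33 = 10.7 mmHg, above the 8 mmHg the trial was sized to detect.

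**How often the result would be undecided.** Take 8 mmHg as a margin, for illustration only. Excluding it at one-sided 5% needs an observed worsening below 8 − 5.33 = 2.67 mmHg. Results between 2.7 and 5.3 mmHg are then non-significant and yet do not exclude 8. With a true difference of 0 the chance of this is 0.950 − 0.800 = 15%. With a two-sided 5% test and a one-sided 2.5% bound it is 0.975 − 0.694 = 28%.

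**Groups.** Group sizes are not stated. Assuming 10 to 30 participants in PD+OH and SD_diff 20, the 95% half-width for its ON–OFF difference runs from 2.262 × 20 / √10 = 14.3 to 2.045 × 20 / √30 = 7.5 mmHg.

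**The case against.** The strongest reply is that the objectives are neutral. Aim 1 is to investigate the effect of levodopa and Aim 2 is to determine whether it differs by group. A trial sized to detect a difference suits both, and the hypothesis sentences may be no more than the investigators' expectations. Aim 1 itself allows for a mild hypotensive effect. This stands in part: the mismatch is between hypotheses and analysis, not between objectives and analysis. It does not remove the gap, because the hypotheses are stated and the plan does not say what would bear them out.

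A reader might infer more than the documents support:

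- That no result could support the hypotheses. This goes too far for Aim 1, whose hypothesis runs in one direction: a significantly smaller drop ON than OFF would support it. It would not support an absence of alteration.
- That the plan means to read p > 0.05 as confirmation. It never says so, and the mixed model will yield an estimate and interval. What is missing is the rule for reading them.
- That 40 is the wrong number. On the reading that reproduces it, 40 also gives 80% power to exclude an 8 mmHg worsening when the true difference is 0. The 46% and 59% miss rates apply only if 20 is the per-measurement SD.
- That group is left out of the secondary models. Their terms are not listed, so group is unspecified there, not excluded.

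**Conclusion.** The concern holds in this form. As written, the plan gives the expected near-zero result no pre-specified interpretation, and a non-significant ON–OFF difference would support neither the no-worsening nor the no-alteration hypothesis. On the reading that reproduces n = 40, a true 8 mmHg worsening goes undetected 20% of the time (31% if the 5% is two-sided), and a result just short of significance is compatible with a worsening of up to about 10.7 mmHg. If 20 mmHg is the per-measurement SD, the miss rates are 46% and 59%. Separately, no ON–OFF contrast by group is specified for Aim 2, and none is specified within PD+OH for the hypothesis about neurogenic orthostatic hypotension.

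The absence of a margin and of a group contrast is read directly from the text. The figures rest on a paired t analysis of 40 complete participants. The 8 mmHg margin and the group sizes of 10 to 30 are illustrative assumptions; the plan gives 8 mmHg only as a difference to detect.

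**What to change.** Before data are seen, amend the Statistical Methods section, and the Objectives where needed:

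1. State that an absence of worsening will be concluded only if the confidence bound for ON minus OFF in ΔSBP-3', from the planned mixed model, excludes a worsening of a stated margin at a stated one-sided alpha. The sponsor must specify and justify the margin. If none can be justified, restate Aim 1 as estimation with a 95% interval.
2. State that a non-significant ON–OFF difference, including a Hochberg-adjusted p > 0.05, supports no conclusion of no worsening or no alteration.
3. For Aim 2, add PD group and a state-by-group term to the mixed models. Report the interaction, and the ON–OFF estimate with its 95% interval within each group.
4. For neurogenic orthostatic hypotension and the baroreflex indices, either report estimates with intervals or pre-specify equivalence bounds for the key indices.

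The cost is wording, the work of justifying a margin, and a small model extension; data collection is unchanged. There are three downsides. An inconclusive interval could no longer be reported as support. Group intervals will be wide. And 40 may be too few: at an illustrative 8 mmHg margin with a true difference of 0, power is 80% only with SD of the difference 20 and one-sided 5%. It is 69% at one-sided 2.5%, and 54% or 41% (one-sided 5% or 2.5%) with SD of the difference 28.3. The sidedness and the meaning of the 20 mmHg should therefore be stated in the same amendment.

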# **Study Population**

Age of Participants: 18+

## Sample Size:

At Utah:

All Centers: 40

#### **Inclusion Criteria:**

## All participants:

- Age 18 or older
- Diagnosis of PD based on consensus criteria (Movement Disorder Society Criteria for Parkinson's disease) [13].

#### For PD+OH group:

- Orthostatic hypotension defined by sustained drop in systolic blood pressure > 20 mmHg and/or a drop in diastolic blood pressure > 10 mmHg within 3 minutes from supine to standing during active standing or tilt [14].
- Autonomic testing and a ratio orthostatic heart rate change / systolic blood pressure change < 0.5 bpm/mmHg will confirm a neurogenic etiology [15].

#### **Exclusion Criteria:**

## Participant exclusion criteria

- Current usage of medications with potential to affect autonomic or sensory testing, in which the medication can't be held 48 hours prior to testing (e.g. antihypertensives, muscle relaxants, stimulants, and some antidepressants that alter sympathetic function). Participants will be instructed to obtain approval from prescribing providers in cases a medication must be held
- Cognitive impairment according to the principal investigator that would limit the ability to follow instructions during testing
- Usage of dopamine agonists -- this class of medication is associated with orthostatic hypotension and residual medication effects may confound the results of the study due to the long half-life
- Contraindication to the Valsalva maneuver (known middle ear damage or disease, Moya-Moya disease, myocardial infarction within 6 months, and retinal detachment within 6 months)

## Design

Prospective Biomedical Intervention or Experiment

## **Study Procedures**

## Recruitment/Participant Identification Process:

- Potential participants with PD will be identified from the movement disorders clinic. The principal investigator ([name]) will be responsible to review charts and medical records to ensure eligibility. Co-investigators listed on the IRB as well as other U of Utah Healthcare providers who have been made aware of the study, may offer enrollment to potential participants in person in a clinic setting. In the event that a patient expresses interest in participating in research, our principal investigator (or approved study personnel) will contact the patient to provide additional information regarding the study.
- Information about the study will also be displayed in the movement disorder bi-annual newsletter. Research study flyers will be available for all patients seen in the movement disorders clinic. The flyers will be available in the waiting room. Participants can also be recruited from the community through local PD Support Groups and word of mouth, and can contact the primary investigator (or approved study personnel) to inquire about screening for the study. Advertisement on the University of Utah study locator website may also be used as a recruitment method.

#### **Informed Consent:**

## Description of location(s) where consent will be obtained:

Consent will be obtained in a dedicated space for clinical assessments of research subjects at University of Utah Headache Clinic (INC), University of Utah Neurology/Neurosurgery Clinic (INC and CNC), or Headache Physiology Laboratory ([name]).

## Description of the consent process(es), including the timing of consent:

The principal investigator (or approved personnel) will obtain consent prior to performing any of the study procedures, and will explain the necessary information to allow the subject to make an informed decision about participation in the study. During the consent process, the background and purpose of the study, the study procedures, review the risks and benefits of the study, and review the process involved in the protection of personal identifiable information will be explained. Inclusion and exclusion criteria for the study will also be reviewed. Participants will have time to discuss any questions or concerns with the principal investigator. Throughout the study, study personnel will also give participants opportunities to ask questions and get more information about the study protocol for ongoing informed consent.

#### **Procedures:**

**Screening:** When the PI (or approved study personnel) makes contact with potential participant, basic information will be obtained to determine eligibility, including: medical history, PD diagnosis date and symptoms, current medications, among others.

Consent Process: Informed consent will be completed. Participants will complete the informed consent form on paper, or via REDCap. Participants will receive a paper copy per their request. Prior to signing the consent form, study personnel will thoroughly explain all study procedures and provide participants with ample time to ask any questions. The study team will continue to provide participants with opportunities to ask questions to ensure ongoing informed consent throughout the progress of the study.

Clinical assessment: The primary investigator will perform a medical history and physical examination before the testing procedures (baseline visit). The baseline visit will be performed on levodopa. The scales and assessments will include the Composite Autonomic Symptoms Score 31 (COMPASS 31), the Movement Disorder Society-Sponsored Revision of the Unified Parkinson's Disease Rating Scale (MDS-UPDRS) part I, II, III, and Hoehn and Yahr stage. The clinical assessment and scales are part of the standard of care in PD. Orthostatic vital signs (standing and supine measures of heart rate and blood pressure) will be performed during the baseline visit with active standing and the day of off-levodopa autonomic testing.

**Autonomic testing:** All participants will undergo autonomic testing on two separate days. The first autonomic testing will occur within 4 weeks of the baseline visit. The two autonomic tests will occur within a 2-week timeframe. To avoid any confounding of treatment effects and period effects, the order of testing (on versus off levodopa) will be randomized so testing on the first day will be on-levodopa for half of the participants and off-levodopa for the other participants. The procedures performed in this study are part of standardized clinical autonomic function testing. Autonomic testing will be performed by a research assistant with expertise in autonomic testing.

Each participant will undergo testing in the on-levodopa state (45min to 1h after taking their regular dose of levodopa in the morning) and off-levodopa state. For testing in the off-state, the last dose of levodopa will be taken at least 12 hours before testing. Off-state in PD is expected to cause some degree of discomfort related to re-emergence / exacerbation of the motor and non-motor symptoms of PD. To limit the duration of the off-state, autonomic testing will be performed early in the morning between 7am and 8am. As soon as the autonomic testing is completed, the participant will be allowed to take levodopa. A participant may not be eligible for the study if the investigator believes that holding levodopa for testing is not safe. Briefly withholding levodopa, and/or medications that can interfere with heart rate or blood pressure measures, on the morning of the test is part of standard clinical autonomic function testing and is known to be well tolerated based on extensive clinical experience of the PI.

Participants will be instructed to have a standardized low-carbohydrate meal in the morning to avoid the confounding effects of postprandial hypotension and instructed to maintain a stable fluid intake to avoid volume shifts.

Autonomic testing will include non-invasive monitoring of blood pressure and heart rate during the Valsalva maneuver and during a 10-minutes head-up tilt.

*Electrocardiogram* (ECG): For monitoring the ECG, electrocardiographic leads are applied to the chest, abdomen, neck, or arms. All participants have ECG monitoring during the Valsalva maneuver and tilt table testing described below. Measurement of beat-to-beat heart rate part of standard clinical autonomic function testing.

Finger blood pressure measurement: A finger cuff is applied for non-invasive measurement of continuous blood pressure. All participants have finger blood pressure monitoring during the Valsalva maneuver and tilt table testing described below. Tracking blood pressure continuously via a finger cuff device is part of standard clinical autonomic function testing.

*Brachial blood pressure*: A clinical automated brachial cuff is applied for measurement of brachial blood pressure. All participants have brachial blood pressure monitoring before and during head-up tilt table testing. Measuring brachial blood pressure is part of standard clinical autonomic function testing.

*Respiration*: A device for continuous monitoring of respiration is applied to the chest. All participants have respiratory monitoring during the experimental manipulations described below, unless technical limitations obviate such monitoring. Monitoring respiration is part of standard clinical autonomic function testing.

Valsalva maneuver: Assessment of beat-to-beat blood pressure and heart rate during and after performance of the Valsalva maneuver is a well-accepted standard autonomic function test. The participant lies supine on a tilt table with head on pillow. The participant blows or strains against a resistance for 12 seconds at 40 mmHg and then relaxes. If a "square wave" phenomenon is observed, the subject may be tilted at 20 degrees head up and the procedure repeated. At least 3 Valsalva maneuvers are done. The maneuvers are repeated (at least 1 minute between repetitions), until a technically adequate recording is obtained. Indices of

baroreflex-cardiovagal and cardiovascular noradrenergic functions are derived from the heart rate and blood pressure responses to the Valsalva maneuver. Indices of baroreflex cardiovagal function include the Valsalva ratio derived from the maximum heart rate generated by the Valsalva maneuver divided by the lowest heart rate occurring within 30 s of the peak heart rate and the slope of the relationship between cardiac R-R interval vs. systolic blood pressure in Phase II of the Valsalva maneuver is taken as a measure of baroreflex-cardiovagal gain (BRS-V). Indices of baroreflex cardiovascular noradrenergic function include the difference in BP between baseline and the end of Phase II, the pressure recovery time (PRT) which is the time from the nadir of the systolic blood pressure in Phase III of the Valsalva maneuver to complete return of systolic blood pressure to baseline, the adrenergic baroreflex sensitivity which is calculated from the slope of the line reflecting the difference of the baseline systolic blood pressure and the lowest systolic blood pressure in Phase III and the areas below the baseline systolic blood pressure calculated in Phase II (BRA-II) and IV (BRA-IV) of the Valsalva maneuver.

Head-up tilt table testing: The participant lies supine for at least 10 minutes after placement of monitoring leads. Baseline hemodynamic measures are taken. Then the participant is tilted head-up to 70 degrees from horizontal using a motorized tilt table. The duration is up to 10 minutes but may be less for safety reasons if the blood pressure decreases rapidly and progressively. Hemodynamic measures are taken at regular interval during and after tilt. Head-up tilt is part of standard clinical autonomic function testing.

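### Test order is not balanced within OH group and the OFF-state group t tests carry no period term, so chance order imbalance adds avoidable error to those comparisons

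*Combined protocol and SAP*

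**What the plan says.** The Sample Size section gives one total, "All Centers: 40", and no number per OH group. The inclusion criteria define PD+OH but set no target or minimum for either group.

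Under Procedures (Autonomic testing), each participant is tested ON and OFF levodopa on two days, in randomised order: "testing on the first day will be on-levodopa for half of the participants and off-levodopa for the other participants". The stated reason is "To avoid any confounding of treatment effects and period effects". The documents describe no stratification or blocking by OH group.

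The Statistical Methods section puts levodopa state and period in the main mixed model for the 3-minute tilt change in systolic pressure. For the group comparison it says that active-standing changes and baroreflex indices "OFF levodopa will be compared between PD+OH and PD-OH with Student t tests". Secondary outcomes get a mixed-effects model whose terms are not listed. No group-by-levodopa term is named for Aim 2.

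**The concern.** The plan treats a visit effect as a real threat: it randomises order because of it and adjusts the main model for it. That protection covers the ON versus OFF contrast. It does not reach the OFF-state comparison of PD+OH with PD-OH, where each participant contributes one OFF measurement, taken at either the first or the second test visit.

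If one group happens to have more OFF-first participants, part of any visit effect (familiarity with the Valsalva maneuver, for example) appears as a difference between groups, and a t test cannot remove it. The interpretation of the OFF-state baroreflex differences is at stake, as is any Aim 2 contrast that leaves period out. The primary ON versus OFF result is not affected.

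**Working it through.** **The plan's own figure.** Inputs from Statistical Methods: a difference of 8 mmHg, "with a within subject standard deviation of 20 mmHg", 80% power and 5% significance. Formula: n = (SD × (z_α + z_power) / δ)².
- One-sided: (20 × (1.645 + 0.842) / 8)² = 38.7, so 39. By noncentral t, n is 41, and power at 40 is 80.0%.
- Two-sided: (20 × (1.960 + 0.842) / 8)² = 49.1, so 50. Power at 40 is 69.4% by noncentral t.

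The 40 reproduces if 20 mmHg is the SD of the paired difference and the test is one-sided, neither of which is stated. It sizes only the pooled ON–OFF contrast, so it gives no precision for a group comparison.

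**Chance order imbalance.** Assume 20 per group, with 20 of the 40 tested OFF first. The number X of OFF-first participants in PD+OH is hypergeometric: P(X = k) = C(20,k) C(20,20−k) / C(40,20).
- P(10) = 0.248; P(9) + P(11) = 0.409; P(8) + P(12) = 0.230.
- 12:8 or worse: 1 − 0.248 − 0.409 = 0.343.
- 13:7 or worse: 0.343 − 0.230 = 0.113.

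A 12:8 split in one group forces 8:12 in the other. The gap in OFF-first share is g = X/20 − (20 − X)/20 = (X − 10)/10, which is 20 points at 12:8 and 30 points at 13:7. For other splits, a gap of at least 20 points has probability 32% (26:14) or 30% (12:28), and at least 30 points 10% or 8%.

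**Error in the OFF-state difference.** The error is period effect × g. The mean of X is 10, so the mean error is zero. No period effect is given, so I take 0 to 1 SD of the index as an assumed range. At 0.5 SD and a 30-point gap the error is 0.5 × 0.30 = 0.15 SD.

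**Added variance.** Var(X) = 20 × ½ × ½ × 20/39 = 2.564, so Var(g) = 2.564/100 = 0.0256. In SD units the variance of the group difference is 1/20 + 1/20 + (period effect)² × 0.0256.
- No period effect: SE = √0.1000 = 0.316.
- 0.5 SD: SE = √0.1064 = 0.326, about 3% larger.
- 1 SD: SE = √0.1256 = 0.354, about 12% larger.

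**Type I error.** In 40,000 simulated trials at each of 20:20, 12:28 and 26:14, the unstratified t test rejected in 4.9–5.1% of null trials for period effects from 0 to 1 SD. Among trials with a gap of at least 30 points:

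| Assumed period effect | Type I error |
|---|---|
| 0.25 SD | 5–6% |
| 0.5 SD | 7–8% |
| 1 SD | 12–14% |

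With order balanced within groups but the t test kept, the rate at 20:20 falls to 4.4% (0.5 SD) and 2.9% (1 SD), because order variation stays in the residual. Stratifying alone therefore leaves the test conservative, and the order term is also needed.

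**Group-by-levodopa contrast.** An OFF-first participant's ON–OFF difference contains plus one period effect, and an ON-first participant's contains minus one. Without a period term, an order gap enters the Aim 2 contrast as 2 × period effect × g.

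**Group sizes.** SE relative to 20:20 is √((1/n₁ + 1/n₂)/0.1). The Background's 30–65% prevalence of nOH would give 12:28 or 26:14.
- 12:28: √(0.1190/0.1) = 1.09.
- 26:14: √(0.1099/0.1) = 1.05.

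**The case against.** The strongest reply is that order is randomised without reference to OH status, so any imbalance is chance and is already covered by the 5% error rate. That stands. A reader might infer that the OFF-state t tests are biased; the documents do not support this, because the error averages zero over randomisations and the overall type I error is nominal. What remains is a loss of precision and a conditional error in the one trial that is run.

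The visit effect may also be small. The plan says "The two autonomic tests will occur within a 2-week timeframe", and it asks for a standardised morning meal and stable fluid intake. This is fair: at 0.25 SD the problem is negligible even with a 30-point gap.

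A reader might take the OFF-state comparison to be the Aim 2 test. It is not: Aim 2 asks whether the levodopa effect differs between groups, and secondary outcomes are assigned a mixed model that may include period. So lost period control for Aim 2 is possible but not shown.

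A reader might also infer that a lopsided split biases the comparison, or that severe imbalance is likely. Unequal groups cost precision only. Unselected recruitment is itself an assumption, since charts are reviewed for eligibility and PD+OH has its own entry criteria.

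Finally, OH may be shown on active standing or tilt, and autonomic testing helps confirm neurogenic origin, so final group may be unknown when order is assigned. This also stands, and the fix has to allow for it.

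**Conclusion.** The point holds as one of efficiency and robustness. Order is balanced overall but not within OH group, and the OFF-state t tests omit the period term that the plan uses elsewhere. At 20 per group there is about a one-in-three chance of a gap of at least 20 points in OFF-first share and about one in nine of at least 30. The average cost is small, about 3% on the standard error at an assumed 0.5 SD period effect. The conditional cost is material only when a large gap meets a large period effect.

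These sizes rest on an assumed period effect and, for the main figures, on 20 per group. The plan should be changed because the remedy is cheap, extends its own safeguard, and the stratified part cannot be added after enrolment.

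**What to change.** 1. Randomise test order in small blocks within provisional OH group. Classify provisionally from the baseline-visit active-standing measurements, which precede both test days, and confirm the final group later under the existing inclusion criteria. The baseline visit is on levodopa, so some reclassification should be expected.
2. Replace the Student t tests on OFF-day measures with a linear model containing final OH group and visit order. The order term also handles imbalance left by reclassification.
3. State that period stays in any mixed model used for the Aim 2 group-by-levodopa contrast.
4. Preferably, state a target or minimum number per OH group for precision. A hard 20:20 cap is a recruitment trade-off, because the faster-filling group would close early, and it is not required.

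Cost: a stratified list, one degree of freedom in each OFF-state model, and some participants whose final group differs from their stratum. Items 1 to 3 need no extra testing and no extra participants.
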